5.2 Description of Safety Analyses

Adverse Events

Adverse events will be graded by the investigator according to the “Guidance for Industry: Toxicity Grading Scale for Healthy Adult and Adolescent Volunteers Enrolled in Preventive Vaccine Trials” as adapted in the Study Protocol. The investigator will also assess causality (relationship to treatment) as *Definitely related*, *Probably related*, *Possibly related*, and *Unrelated*. AEs will also be coded using the Medical Dictionary for Regulatory Activities version 23 or higher (MedDRA®). Treatment-emergent AEs (TEAEs), defined as any AE that occurs after a patient receives the first dose of the assigned study treatment, will be summarized by the number and proportion of patients reporting at least one occurrence of the AE. Frequencies and rates of each TEAE will be summarized by MedDRA preferred term within system organ class (SOC), by severity grade, and relation to treatment for each treatment group. The rate calculation will be based on the number of patients in the Safety population for the relevant treatment group.

Treatment emergent serious adverse events (TESAEs) will be summarized and displayed by frequency and rate by MedDRA preferred term within SOC.

A by-patient AE data listing of all adverse events including verbatim term, coded term, grade, and relation to study treatment will be provided.

Laboratory Tests

Clinical laboratory tests will be performed at the times prescribed in the protocol. The following clinical laboratory tests will be analyzed:

Hematology:

Hemoglobin, hematocrit, complete white blood count (total and differential), platelet count, random blood glucose, total cholesterol, HDL, LDL, and triglycerides.

Clinical Chemistry:

AST, ALT, GGT, alkaline phosphatase, bilirubin (total and direct), BUN, creatinine, sodium, potassium, and chloride.

Urinalysis:

Appearance, glucose, protein, and blood.

Clinical laboratory results and the change from baseline (CFB, baseline defined as the value at the baseline visit) will be summarized for the Safety population with summary statistics (mean, standard deviation, n, minimum, median, maximum) by time point for each treatment group. Clinical laboratory results will be classified as "Normal", or "Abnormal"; "Abnormal" results will be further classified by the PI as "Clinically significant" (CS) or "Not clinically significant" (NCS). Clinical laboratory results will be summarized by a shift table from baseline with categories "Normal", "Abnormal (NCS)", and "Abnormal (CS)".

All clinically significant abnormal laboratory findings will be reported as AEs. All AEs recorded will be listed.

Physical Exam

Physical exams (PEs) will be performed as outlined in the protocol. All clinically significant abnormal PE findings will be recorded as AEs. All physical exam data will be listed as shown in Appendix B.

Vital Signs

Vitals signs will include weight, heart rate, respiratory rate, blood pressure (diastolic and systolic), and temperature. Vital signs will be taken as outlined in the protocol. The baseline visit vital signs will be used for baseline for changes at the Week 3 and Week 6 follow-up visits. If repeat vital signs are taken at a given time point, then the last measurement will be used for the analysis tables.

Vital signs and CFB will be summarized for the safety population with summary statistics (mean, standard deviation, n, minimum, median, maximum) by time point and treatment group. All vital signs will be listed.

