5.9. Plan for Laboratory Safety Tests

A central laboratory will be used for laboratory safety testing. Blood tests will include hemoglobin, hematocrit, complete blood count (total and differential), platelet count, random blood sugar, total cholesterol, HDL, LDL, triglycerides, albumin, AST, ALT, GGT, alkaline phosphatase, bilirubin (total/direct), BUN, creatinine, sodium, potassium, chloride. Routine urinalysis will include appearance, glucose, protein, and blood.

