10. ADVERSE EVENTS

The term “adverse event” is defined for purposes of this study as any unwanted physical, psychological or behavioral change experienced by a subject during the course of the study and after taking the first dose of study medication regardless of its severity or relation to the study. Adverse events may include symptoms, signs, unexpected worsening of pre-existing conditions, clinically significant changes in laboratory values, diseases and syndromes, and significant and unexpected failures of pharmacological action of other medications. Symptoms of VRIs (cough, sore throat, nasal obstruction, fatigue, headache, myalgia, feverishness) and complications of VRIs will not be reported as adverse events.

Adverse events will be recorded on the appropriate EDC forms throughout the study, and the severity of each adverse event will be graded on a four-point scale: mild, moderate, severe, or life-threatening (See [Appendix II](#)). The duration of the adverse event and relationship to the study drug will also be recorded. All adverse events must be followed until their resolution or stabilization even beyond the planned study period.

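### Albumin is collected and graded but missing from the SAP's list of laboratory tests to analyse; a laboratory table by toxicity grade would be a cheap addition

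*SAP*

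**What the plan says.** **Albumin.** Protocol 5.9 includes it in the central-laboratory blood panel: "random blood sugar, total cholesterol, HDL, LDL, triglycerides, albumin, AST, ALT, GGT". The Synopsis and Protocol 5.2 and 5.5 put safety bloods at baseline, Week 3 and Week 6. Appendix II Table 13 gives albumin Grades 1 to 3, with Grade 3 below 2.5 g/dL and no Grade 4.

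SAP 5.2 names the tests to be analysed in two blood lists. The hematology list, which also holds glucose and lipids, ends "platelet count, random blood glucose, total cholesterol, HDL, LDL, and triglycerides". The clinical chemistry list is "AST, ALT, GGT, alkaline phosphatase, bilirubin (total and direct), BUN, creatinine, sodium, potassium, and chloride". Albumin is in neither.

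**Grades.** SAP 5.2 gives laboratory data summary statistics by time point and arm, and then: "Clinical laboratory results will be summarized by a shift table from baseline with categories" normal, abnormal (NCS) and abnormal (CS). The split within abnormal values is the investigator's: abnormal "results will be further classified by the PI as" CS or NCS.

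A laboratory value becomes an adverse event through that call. The SAP says "All clinically significant abnormal laboratory findings will be reported as AEs", and Protocol 10 counts among adverse events "clinically significant changes in laboratory values, diseases and syndromes". Toxicity grades attach to adverse events: "Adverse events will be graded by the investigator according to the" FDA scale adapted in Appendix II.

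**The concern.** There are two separate points, and they differ in weight.

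First, a test that the protocol collects and grades has no planned analysis. If the SAP is programmed as written, the report will contain no albumin summary statistics and no albumin shift.

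Second, the grade of a laboratory value reaches a table only if an investigator first calls the value clinically significant. The values come from one central laboratory and the protocol prints numeric limits for most tests, so a uniform count per arm of severe values could be programmed. As planned, the tabulated count depends on calls made site by site, or has to be assembled from listings. Minimum and maximum show that an extreme value occurred, not how many subjects had one.

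**Working it through.** The plan states no figure to reproduce here. The check compares lists and traces one value through the rules.

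**Step 1: compare the blood panels.** Count the differential within the blood count, and total and direct bilirubin as one item.

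| Source | Items | Albumin |
|---|---|---|
| Protocol 5.9 | 20 | yes |
| SAP 5.2 hematology | 9 | no |
| SAP 5.2 clinical chemistry | 10 | no |

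The SAP total is 9 + 10 = 19, and 20 − 19 = 1. The missing item is albumin. Urinalysis matches, 4 items against 4. The SAP keeps the protocol's order and divides it after triglycerides; albumin stands exactly at that division, between triglycerides and AST. The SAP revision history does not mention dropping it. Both facts point to a slip in splitting the list.

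Each subject is due 3 albumin results. At the expected 2,842 subjects and full attendance that is 3 × 2,842 = 8,526 results, one third of them baseline. This is an upper bound on unsummarised data, not a measure of harm.

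**Step 2: trace a Grade 3 or 4 value judged NCS.**

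- Adverse event? No. Protocol 10 and SAP 5.2 bring in clinically significant findings only.
- Graded tables? SAP Section 8 has two that show toxicity grade, 14.3.1.1 and 14.3.1.3. Both are restricted to treatment-emergent adverse events, so the value enters neither.
- Laboratory tables? There are six, 14.3.2.1 to 14.3.4.2: three of summary statistics and three of shifts. None of the six uses grade. The value falls in the NCS shift cell with minor abnormalities and may set a minimum or maximum.
- Listings? Listings 16.2.8.1 to 16.2.8.3 can show it, though their contents are not specified.

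The value is therefore visible, but counted in no table by grade.

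**Step 3: can grades be programmed?** Of the 20 blood items, 4 have only narrative limits in Appendix II (hematocrit, HDL, LDL, chloride), so 20 − 4 = 16 have a numeric Grade 3 limit for at least one component. If the differential and direct bilirubin are counted separately there are 22 items. Direct bilirubin has no scale of its own, while the differential has limits for some cell types, which gives 22 − 5 = 17.

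**Step 4: do the printed bands cover every value?** Not at the boundary between Grades 2 and 3, which decides a count of Grade 3 or higher:

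| Test | Grade 2 | Grade 3 | Problem |
|---|---|---|---|
| ALT, AST (× ULN) | 2.6–5.0 | 5.1–10 | gap 5.0 to 5.1 |
| Alkaline phosphatase (× ULN) | 2.1–3.0 | 3.1–10 | gap 3.0 to 3.1 |
| Bilirubin, liver test raised (× ULN) | 1.26–1.5 | 1.51–1.75 | gap 1.5 to 1.51 |
| Bilirubin, liver test normal (× ULN) | 1.6–2.0 | 2.0–3.0 | overlap at 2.0 |
| Platelets (per mm³) | 100,000–124,000 | 25,000–99,000 | gap 99,000 to 100,000 |

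A programmed table needs a stated rule for these values.

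**The case against.** The strongest reply concerns the second point. Appendix II is headed as grading for adverse events, and Protocol 10 and 10.1 apply it to those. The Synopsis names adverse events as the safety parameter, and Protocol 8.4.3 asks only for descriptive safety analyses. A laboratory table by grade was never promised, so its absence contradicts nothing. Appendix II also calls its laboratory limits guidelines, and some Grade 3 limits are mild, such as potassium of 5.5 mEq/L. A filter of clinical judgement is a reasonable response to such a scale. All of this stands, and it is why the second point is offered as an improvement.

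On albumin, the reply is that the gap is clerical and that a clinically significant low albumin would still be reported and graded as an adverse event. Both are fair, but the routine summary is still absent.

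A reader might infer three stronger things that the documents do not support:

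- **Severe laboratory values vanish from the report.** They do not; Step 2 shows where they remain. Listing 16.2.8.2 may also include albumin.
- **Investigator judgement favours one arm.** Protocol 6 masks investigators and the laboratory to allocation. The issue is inconsistent counting across sites, not a demonstrated bias.
- **A stated number of severe cases will be missed.** The documents give neither the rate of Grade 3 or 4 values nor the share that would be judged NCS. If that share is zero, nothing is missed.

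The SAP refers to a Table Requirements Document and an Appendix B that are not among the documents reviewed. They may add detail, but the Section 8 index has no laboratory table by grade.

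**Conclusion.** The albumin point holds as an error in the SAP: one of 20 protocol blood tests is left out of the analysis list with no reason given. The grading point holds as a description of the plan, but only as a suggestion. It assumes that the SAP is followed literally and that the unseen layouts add no table beyond the Section 8 index. No size of effect is claimed for either part. Sample size, alpha and efficacy conclusions are untouched. Severity is minor.

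**What to change.** **1. Albumin.** Add it to the clinical chemistry list in SAP 5.2, so that it enters Tables 14.3.3.1 and 14.3.3.2. This costs one word.

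**2. Optional graded table.** Add one descriptive table by arm, with no test: baseline grade against worst post-baseline grade, with a row for Grade 3 or higher. Program it from the numeric limits in Appendix II Tables 13 and 14 and the central laboratory's reference ranges, using unscheduled as well as scheduled samples. Keep all existing tables. State these rules in advance:

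- Include only tests with numeric limits. Leave out hematocrit, HDL, LDL, chloride, direct bilirubin and differential cells without a scale.
- A value between two printed bands takes the higher grade. Thus anything above the Grade 2 upper limit, or below the Grade 2 lower limit for decreases, counts as Grade 3.
- Where bands overlap (bilirubin at exactly 2.0 × ULN), say which grade applies. The higher grade is consistent with the rule for gaps.
- Choose the bilirubin scale by whether a liver test in the same sample is raised, and use the random scale for glucose.
- Combine Grades 3 and 4 where Grade 4 is clinical or blank (high glucose, BUN, eosinophils, albumin).
- For hemoglobin, use the absolute scale in the shift and show the fall from baseline as a separate row.

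The cost is a little programming on data already collected. The downside is that some minor excursions will be counted as Grade 3, because the limits are guidelines; a footnote should say so.

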6.0 Other Relevant Data Analyses/Summaries

6.1 Patient Completion

A table will be constructed with counts and percentages by treatment assignment of subjects' disposition status, including the reason for withdrawal for all subjects who

withdrew. Percentages will be computed relative to the number of subjects randomized to each treatment.

6.2 Prior and Concomitant Medications

All prior/concomitant medications taken by or administered to a patient will be collected from the 30 days prior to treatment through the completion of the follow-up visit. Concomitant medications will be coded using the most recent version of the WHO Drug Dictionary. A data listing for concomitant medications including ATC Levels I and IV will be provided.

6.3 Death Report

The number and percentage of deaths from all causes will be computed by treatment group for the safety population. All death report data will be listed.

6.4 Additional Baseline Data

Medical history will be presented in data listings for the safety population. History events will be coded using the current version of MedDRA (version 23 or higher).

6.5 Protocol Deviations

Tables will be constructed to summarize major and minor protocol deviations by treatment group for the safety population. All protocol deviations will be listed.

6.6 Treatment Compliance and Administration

Treatment compliance data will be summarized by treatment group for the safety population. All treatment compliance and administration data will be listed.

8.0 List of Analysis Tables, Figures and Listings

Table No.	Table Title
14.1.1.1	Subject Disposition Summary by Treatment and Overall (All Subjects)
14.1.2.1	Summary of Major Protocol Deviations (Safety Population)
14.1.2.2	Summary of Minor Protocol Deviations (Safety Population)
14.1.3.1	Summary of Demographic Categorical Variables by Treatment and Stratum (Safety Population)
14.1.3.2	Summary of Demographic Quantitative Variables by Treatment and Stratum (Safety Population)
14.1.4	Summary of Treatment Compliance (Safety Population)
14.2.1.1	Cochran-Mantel-Haenszel Test Results: COVID-19 Status (ITT Population)
14.2.1.2	Cochran-Mantel-Haenszel Test Results: Symptomatic COVID-19 Subject Status with Best-Case and Worst-Case Analysis of Missing Data (ITT Population)
14.2.1.3	Cochran-Mantel-Haenszel Test Results by Sex: Symptomatic COVID-19 Subject Status with Tipping Point Analysis of Missing Data (ITT Population)
14.2.1.4	Cochran-Mantel-Haenszel Test Results by Sex: Symptomatic COVID-19 Subject Status (ITT Population)
14.2.1.5	Cochran-Mantel-Haenszel Test Results by Age Group: Symptomatic COVID-19 Subject Status (ITT Population)
14.2.1.6	Cochran-Mantel-Haenszel Test Results by Race: Symptomatic COVID-19 Subject Status (ITT Population)
14.2.1.7	Pearson Chi-square Test Results by Stratum: COVID-19 Status (ITT Population)
14.2.1.8	Cochran-Mantel-Haenszel Test Results: VRI Status (ITT Population)
14.2.1.9	Cochran-Mantel-Haenszel Test Results: Symptomatic VRI Subject Status with Best-Case and Worst-Case Analysis of Missing Data (ITT Population)
14.2.1.10	Cochran-Mantel-Haenszel Test Results: Symptomatic VRI Subject Status with Tipping Point Analysis of Missing Data (ITT Population)
14.2.1.11	Cochran-Mantel-Haenszel Test Results by Sex: Symptomatic VRI Subject Status (ITT Population)
14.2.1.12	Cochran-Mantel-Haenszel Test Results by Age Group: Symptomatic VRI Subject Status (ITT Population)
14.2.1.13	Cochran-Mantel-Haenszel Test Results by Race: Symptomatic VRI Subject Status (ITT Population)
14.2.1.14	Pearson Chi-square Test Results by Stratum: VRI Status (ITT Population)

Table No.	Table Title
14.2.2.1	Cochran-Mantel-Haenszel Test Results: COVID-19 Related Mortality Status (ITT Population)
14.2.2.2	Pearson Chi-square Test Results by Stratum: COVID-19 Related Mortality Status (ITT Population)
14.2.3.1	Cochran-Mantel-Haenszel Test Results: COVID-19 Antibody Test Status (ITT Population)
14.2.3.2	Pearson Chi-square Test Results by Stratum: COVID-19 Antibody Test Status (ITT Population)
14.2.3.3	Cochran-Mantel-Haenszel Test Results: VRI Related Hospitalization Status (ITT Population)
14.2.3.4	Pearson Chi-square Test Results by Stratum: VRI Related Hospitalization Status (ITT Population)
14.2.3.5	Cochran-Mantel-Haenszel Test Results: VRI Related Mortality Status (ITT Population)
14.2.3.6	Pearson Chi-square Test Results by Stratum: VRI Related Mortality Status (ITT Population)
14.2.3.7	Cochran-Mantel-Haenszel Test Results: ARI Incidence Status (ITT Population)
14.2.3.8	Pearson Chi-square Test Results by Stratum: ARI Incidence Status (ITT Population)
14.2.3.9	Cochran-Mantel-Haenszel Test Results: ARI Related Hospitalization Status (ITT Population)
14.2.3.10	Pearson Chi-square Test Results by Stratum: ARI Related Hospitalization Status (ITT Population)
14.2.3.11	Cochran-Mantel-Haenszel Test Results: ARI Related Mortality Status (ITT Population)
14.2.3.12	Pearson Chi-square Test Results by Stratum: ARI Related Mortality Status (ITT Population)
14.3.1.1	Treatment Emergent Adverse Events Summary: Total AE, Toxicity Grade, Relationship to Treatment, Serious AEs by Treatment (Safety Population)
14.3.1.2	Treatment Emergent Adverse Events by System Organ Class, Preferred Term, and Treatment (Safety Population)
14.3.1.3	Treatment Emergent Adverse Events by System Organ Class, Preferred Term, Treatment, and Toxicity Grade (Safety Population)
14.3.1.4	Treatment Emergent Adverse Events by System Organ Class, Preferred Term, Treatment, and Relationship to Treatment (Safety Population)
14.3.1.5	Treatment Emergent Serious Adverse Events by System Organ Class, Preferred Term, and Treatment (Safety Population)
14.3.2.1	Clinical Laboratory Summary Statistics: Hematology (Safety Population)

Table No.	Table Title
14.3.2.2	Clinical Laboratory Shift Tables: Hematology (Safety Population)
14.3.3.1	Clinical Laboratory Summary Statistics: Clinical Chemistry (Safety Population)
14.3.3.2	Clinical Laboratory Shift Tables: Clinical Chemistry (Safety Population)
14.3.4.1	Clinical Laboratory Summary Statistics: Urinalysis (Safety Population)
14.3.4.2	Clinical Laboratory Shift Tables: Urinalysis (Safety Population)
14.3.5.1	Vital Signs Summary Statistics (Safety Population)

Listing No.	Data Listing Title
16.2.1	Subject Disposition Listing (All records)
16.2.2	Protocol Deviations Listing (Safety Population)
16.2.3	Patients Excluded from the Efficacy Analysis (Safety Population)
16.2.4.1	Subject Demographics Listing (Safety Population)
16.2.4.2	Medical History Listing (Safety Population)
16.2.4.3	Concomitant Medications Listing (Safety Population)
16.2.5.1	Treatment Compliance Listing (Safety Population)
16.2.5.2	Drug Concentration Data Listing (Safety Population)
16.2.6.1	Subject Primary Efficacy Variables Listing: COVID-19 Status, VRI Status (Safety Population)
16.2.6.2	Subject Secondary Efficacy Variables Listing: ARI Status, Hospitalization Status (Safety Population)
16.2.6.3	SARS-CoV-2 Antibody Status (Safety Population)
16.2.7.1	Adverse Events Listing (Safety Population)
16.2.7.2	Subject Deaths Listing (Safety Population)
16.2.8.1	Hematology Listing (Safety Population)
16.2.8.2	Clinical Chemistry Listing (Safety Population)
16.2.8.3	Urinalysis Listing (Safety Population)
16.2.9.1	Physical Examination Listing (Safety Population)
16.2.9.2	Vital Signs Listing (Safety Population)
